## Data Collection

Veterans: Assessment will occur at the following time points:

- In person study visits at Baseline, 6, and 12 months: Veterans will meet with research staff to complete surveys (described below), weight, height (Baseline only), blood pressure and waist circumference measurement, and blood tests (Baseline, 6, and 12 months only). If circumstances restrict in-person visits (e.g. COVID or if Veteran opts for a remote visit, the weight and waist circumference will be obtained via telephone/video. Height and blood pressure will be obtained through the patient's most recent VA visit from the electronic medical record. The Baseline will include a survey (completed before receiving PAL Intervention/Enhanced Usual Care). Veterans will receive accelerometers (described below). Electronic chart review will also occur at these time points. At 6 months, Veterans in the intervention arm will participate in a short qualitative interview as part of the RE-AIM evaluation Telephone Coaching Calls (Veterans in PAL Intervention arm only): Health coaches will use a counseling tool that also facilitates data collection.

Chart reviews (24 months post-baseline visit) to explore maintenance of weight and focus groups post-

## intervention

PACT Teams: At 6 and 12 months, we will give surveys to PCPs and audiotape select visits.

## Measures

All variables described below will be collected and analyzed by research staff. Core measures are listed and described below. Baseline surveys have been pilot tested in 45 Veterans.

**BASELINE DEMOGRAPHIC DATA** – We will collect socio-demographic information, health literacy (2-item screen), and depression (PHQ970) via surveys. Co-morbidities will be determined via electronic chart review.

### AIM 1: WEIGHT AND CLINICAL OUTCOMES –

- Weight & Height: RAs (in-person visit) will obtain Veteran weight measurements using a standardized protocol which includes: 1) weighing without shoes or heavy garments using a digital scale that will be calibrated monthly; 2) at each study time point (Baseline, 6, and 12 months). Height will be measured with a stadiometer and rounded up to the nearest half-centimeter, at Baseline only.
- RAs (remote visit) will obtain Veteran weight measurements via telephone/video using a standardized protocol which includes: 1) weighing without shoes or heavy garments using a digital scale; 2) at each study time point (Baseline, 6, and 12 months). Height will be obtained through chart review. Waist Circumference: Waist circumference will be measured using procedures adapted from National Health and Nutrition Examination Survey (NHANES). RAs (in-person visit) will measure to the nearest quarter inch at the high point of the iliac crest at minimal respiration. This will be measured at Baseline, 6, and 12 months. RAs (remote visit) will guide the Veteran on how to take the waist circumference measurement and obtain measurements through telephone/video.
- Blood Pressure: RAs (in-person visit) will obtain 2 blood pressure measurements using an automated sphygmomanometer (Omron HEM-907XL). The cuff will be placed on the Veteran's left upper arm, with the bottom of the cuff placed approximately 1 in above the crook of the elbow as per a standard protocol. RAs (remote visit): Blood pressure will be obtained through chart review from the Veteran's most recent visit to the VA.

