#### Project Methods

To achieve these objectives, we will conduct a cluster randomized controlled trial of 17 PACTs (randomized at the provider level) and 520 of their overweight or obese Veteran patients at the Brooklyn campus of the NY Harbor Healthcare System to study the impact of the 12-month PAL intervention when compared to Enhanced Usual Care. Patients in the PAL intervention will complete the GEM tool and receive health coaching, followed by telephone coaching from the health coach over 12 months. The GEM

tool is a mobile-friendly software program designed to be delivered on tablet computers in the clinic setting to assess lifestyle behaviors and barriers, provide tailored advice and patient education materials, create initial weight loss and behavior change goals, and facilitate counseling by the health coach and PACT staff. Patients in the Enhanced Usual Care arm will receive patient education materials (standard VA Healthy Living Messages) and information on the MOVE! program. All patient participants will attend follow-up visits at 6- and 12-months to assess Body Mass Index, waist circumference, blood pressure, diet, blood tests, physical activity, and goal attainment. PACT staff and health coach outcomes will include 5As-related competency, as well as quality and frequency of counseling. If circumstances restrict the availability of in-person visits (e.g. COVID-19) or based on Veteran's preference, this study will provide a remote/tele-visit option for the baseline and follow up visits.

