During the baseline visit we will encourage patients to sign-up for MyHealtheVet, if they have not already done so. If patients are signed-up for MyHealtheVet, they can choose to receive reminders for their upcoming study visits or health coach phone calls electronically via myHealtheVet. Alternatively, patients can choose to receive reminder phone calls from secure VA phones lines. Before upcoming phone coaching calls and study visits, we will send reminders via the secure messaging system MyHealtheVet or make phone calls via secure VA phone lines.

At the end of the visit, the Health Coach will enter a research note into the CPRS system detailing the patient's goals and other important information in the form of a provider report for the provider to review (generated by the tool). At a later date, the patient will meet with a PACT member (either the PCP or another participating PACT member) during their regularly scheduled PC visit who will review the goals and agree on them and/or modify their goals based on a collaborative discussion and conduct brief motivational interviewing to address potential barriers (3-5 minutes). The PACT member will summarize this interaction in a specific CPRS note. Also, over the next 12 months of the intervention, the PACT teamlet will receive CPRS reminders to discuss the goals with the patients when they return for their regularly scheduled PC visits. Patients will follow up with VA resources if indicated/desired. PAL intervention participants will return for separate 6 and 12 month follow-up study visits to measure intermediate behavior change and weight outcomes.

If circumstances restrict the availability of in-person visits (e.g. COVID-19) or based on Veteran's preference, this study will provide a remote/tele-visit option for the baseline, 6 and 12 month follow up visits. For the remote baseline visit, a scale, a tape measure for the waist circumference, informed consent form documents, and the study resource materials will be mailed to the participant. Participants who enroll via a remote visit will have IRB approval for written consent documentation to be waived and a verbal assent will be obtained through telephone/video confirmation by reading the informed consent form to the participant. Through the verbal assent process, the study will document in the patient's medical records on the willingness to be contacted for future research about similar weight loss management research.

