- *Enhanced Usual Care:* Participants will complete the same consenting materials and Baseline Survey as the intervention group. Instead of the completing the PAL tool and receiving health coaching, they will receive

weight management handouts (Healthy Living Messages handouts and MOVE! handouts) as well as information about intensive weight management programs at the VA including MOVE! Participants will follow-up with their PACT teamlets as needed when they return for their regularly scheduled PC visits. Patients will follow up with VA resources if indicated/desired. Enhanced Usual Care participants will return for separate 6 and 12 month follow-up study visits to measure intermediate behavior change, and weight outcomes.

If circumstances restrict the availability of in-person visits (e.g. COVID-19) or based on Veteran's preference, this study will provide a remote/tele-visit option for the baseline, 6 and 12 month follow up visits. For the remote baseline visit, a scale, a tape measure for the waist circumference, the informed consent forms, and the resource materials will be mailed to the participant. Participants who enroll via a remote visit will have IRB approval for consent documentation to be waived and verbal assent will be obtained through telephone/video confirmation by reading the informed consent form to the participant. Through the verbal assent process, the study will document in the patient's medical records on the willingness to be contacted for future research about similar weight loss management research.

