## MEASUREMENTS

Assessment will occur at the following time points:

- A. Baseline study visit:
  - a. In person: baseline survey, basic physical measurements (weight, height, waist circumference, and blood pressure).
  - b. Remote visit: baseline survey, basic physical measurements (weight and waste circumference) via telephone/video, height and blood pressure results through chart review
- B. Follow-up study visits at 6 and 12 months:
  - a. In person visit: Follow-up in-person questionnaire and basic physical measurements (weight, waist circumference, blood pressure).
  - b. Remote visit: Follow-up questionnaire, basic physical measurements (weight and waist circumference) via telephone/video, blood pressure results through chart review
- C. Follow-up telephone calls (only patients in PAL intervention): Follow-up telephone questionnaire
- D. Chart review: This will occur periodically to assess MOVE! attendance, PACT teamlet visits (documentation of weight management-related conversations), and medical co-morbidities. Outcomes will be assessed through chart review up to 2 years after the baseline visit.

Baseline Data: Prior to the intervention, patients will receive a Baseline survey. To evaluate recruitment for the intervention, baseline data including socio-demographic information, perceived health status, health literacy, perceived environmental factors, and depression will be collected. Co-morbidities will be determined through chart review of the electronic medical record. We will also collect health-related attitudes, beliefs, and baseline behaviors.

Weight & Height: In person visit, study personnel will obtain patient weight measurements using a standardized protocol which includes; 1) weighing without shoes or heavy garments using a digital scale that will be calibrated monthly; at each study time point (Baseline, 6, and 12 months). 2) Height will be measured using the primary care clinic stadiometer and rounded up to the nearest half-centimeter at Baseline. For remote visits, study personnel will obtain Veteran weight measurements via telephone/video using a standardized protocol which includes: 1) weighing without shoes or heavy garments using a digital scale; 2) at each study time point (Baseline, 6, and 12 months). Height will be obtained through chart review.

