**Waist Circumference:** Waist circumference will be measured using procedures adapted from National Health and Nutrition Examination Survey (NHANES). In person visit, study personnel will use measuring tape to the nearest quarter inch at the high point of the iliac crest at minimal respiration. This will be measured at baseline, 6, and 12 months. For remote visits, study personnel will guide the Veteran on how to take the waist circumference via telephone/video.

**Blood Pressure:** Study personnel will obtain 2 blood pressure measurements using an automated sphygmomanometer (Omron HEM-907XL). The cuff will be placed on the Veteran's left upper arm, with the bottom of the cuff placed approximately 1|| above the crook of the elbow as per a standard protocol. For remote visits, study personnel will obtain blood pressure through chart review from the Veteran's most recent visit to the VA.

**Feasibility:** We will use process measures from direct observation to determine the feasibility of implementing the PAL intervention at the initial visit. Data on the time to complete the PAL tool, number and types of goals made, number of patients reporting that their PACT teamlets engaged in goal setting conversations, number of reminders completed by the PACT teamlets, time spent doing the intervention, the impact of the intervention on workflow (physician report, qualitative interviews) will be collected. At 6 months into the study period, participating PACT teamlet staff will complete an attitudes survey based on one we have used previously pertaining to intervention implementation. We will also perform qualitative interviews with providers. We will use chart review to note the number of times patients in the telephone support arm actually receive telephone counseling.

**Acceptability:** We will collect data on patient satisfaction with the intervention and the overall visit using patient and provider surveys. We will conduct interviews with participating providers to obtain qualitative data on acceptability.

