#### Data Storage/Security

- *Research Activities:* The following will all take place in private room at the Brooklyn VA with the PI and/or research staff – filling in consent forms, using PAL tool, receiving weight management information, receiving weight management counseling, completing survey measures.
- *Storage of data:* All written data will be kept in locked filing cabinets in a locked room only accessible by the PI and approved study personnel and all electronic data (including survey responses, audio files, and responses to online tool) on secure local VA servers and only accessible on VA password protected computers by the PI and study personnel. Original audio files will be removed from recorders. The data key link will be maintained as a password-protected Excel datasheet on a secure VA Harbor computer within a locked VA Harbor office by the PI, and destroyed upon completion of the final study dataset. The data key link will be kept separate from all survey responses. Only study investigators will perform data entry, access either the surveys or datasets, or perform any analysis of the dataset.
- *Transcription:* For transcription of audio files, files will be sent as encrypted files through the secure server to the VA-contracted transcription company, Transcription Outsourcing, LLC. Transcripts will be de-identified by leaving all identifiable information out of the transcript and using only a unique coded identifier generated by the Principal Investigator. This unique identifier will not use any identifying information (i.e. it will not be generated using the subject's social security number, name, etc.) Recorded information will be transferred to Transcription Outsourcing via a HIPAA-compliant web portal using a VA computer. The transcripts will then be stored and analyzed on a VA secure server. This transcription procedure was approved by the IRB previously (MIRB 01333) under the consultation of the ISO and PO.

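### Remote-visit blood pressure comes from the chart with no date limit, so a 6- or 12-month value can predate treatment

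*Combined protocol and SAP*

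**What the plan says.** Blood pressure is one of the clinical outcomes under hypothesis 1b in the Specific Aims Analysis. At an in-person visit, staff take two readings with an automated device. At a remote visit they take none.

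- Measures, Aim 1, Blood Pressure (remote visit): "Blood pressure will be obtained through chart review from the Veteran's most recent visit to the VA".
- Data Collection, which covers baseline, 6 and 12 months: "Height and blood pressure will be obtained through the patient's most recent VA visit from the electronic medical record".
- Measurements, Blood Pressure: "For remote visits, study personnel will obtain blood pressure through chart review from the Veteran's most recent visit to the VA".
- Measurements, follow-up visits at 6 and 12 months: "Remote visit: Follow-up questionnaire, basic physical measurements (weight and waist circumference) via telephone/video, blood pressure results through chart review".

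The remote option is not confined to emergencies. Project Methods says that when circumstances restrict in-person visits or "based on Veteran's preference, this study will provide a remote/tele-visit option for the baseline and follow up visits".

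None of these places sets a maximum age for the reading, requires it to fall after baseline, or bars one reading from serving two time points. Data Collection says that chart review happens at the study time points, but that dates the review and not the reading. The analysis sections have no rule on the date of a chart value.

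**The concern.** The most recent VA visit before a remote follow-up need not lie after baseline. If the Veteran has had no VA visit since baseline, the rule returns a reading from baseline or earlier. If baseline was remote too, the same reading serves both time points and the change is exactly zero. Sparse attenders are eligible, since entry asks for only one visit with the provider in the past 24 months.

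Such a value enters the mixed model, the Mann-Whitney comparison of arms and the within-arm Wilcoxon test as an observed outcome. The planned multiple imputation, inverse-probability weighting, pattern-mixture analyses and observed/not-observed indicator act only on missing values, so none of them can correct it. A null blood pressure result could then reflect old readings, and the data as collected would not show it.

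**Working it through.** **No figure to reproduce.** The documents give no power, effect size or SD for blood pressure. What follows is a guide to size.

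**Inputs.** L = 3.6 primary care visits per year (Background, PACT). T = 0.5 or 1 year. Assumptions: every such visit yields a reading, and other VA visits are ignored. The remote share r is not given, so it is varied.

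**Step 1: share of remote values with no visit since baseline.**
- Evenly spaced visits: max(0, 1 − LT). Spacing is 365.25/3.6 = 101 days, shorter than either interval, so the share is 0.
- Randomly timed (Poisson) visits: exp(−LT) = exp(−1.8) = 0.165 and exp(−3.6) = 0.027.
- Visit rates that vary between Veterans (negative binomial, assumed shape k): (k/(k + LT))^k. For k = 2, (2/3.8)² = 0.277 and (2/5.6)² = 0.128. For k = 1, 1/2.8 = 0.357 and 1/4.6 = 0.217.

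**Step 2: share of the effect that remote values keep.**
- Immediate, constant effect: 1 minus the Step 1 share. Poisson gives 83.5% at 6 months and 97.3% at 12 months.
- Effect building linearly over 12 months, where a reading of age a keeps (T − a)/T of the effect, or none if it predates baseline:
  - Even spacing: 1 − 1/(2LT) = 0.722 and 0.861.
  - Poisson: 1 − (1 − exp(−LT))/(LT) = 0.536 and 0.730.
  - k = 2: 1 − 1/(1 + LT/2) = 0.474 and 0.643.
  - k = 1: 1 − ln(1 + LT)/(LT) = 0.428 and 0.576.

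| Visit pattern | No visit since baseline, 6 mo | 12 mo | Linear effect kept, 6 mo | 12 mo |
|---|---|---|---|---|
| Evenly spaced | 0% | 0% | 72% | 86% |
| Poisson | 16.5% | 2.7% | 54% | 73% |
| Neg. binomial, k = 2 | 27.7% | 12.8% | 47% | 64% |
| Neg. binomial, k = 1 | 35.7% | 21.7% | 43% | 58% |

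**Step 3: sensitivity to the visit rate (Poisson).** The Step 1 shares become 36.8% and 13.5% at 2 visits a year, and 5.0% and 0.2% at 6 a year.

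**Step 4: whole trial.** Multiply the Poisson share by r. For r = 25%, 50% and 75% this gives 4.1%, 8.3% and 12.4% of all 6-month values, and 0.7%, 1.4% and 2.0% of all 12-month values. For the linear effect at 12 months, the trial keeps 1 − r × (1 − share kept). At r = 25% that is 1 − 0.25 × 0.27 = 93% (Poisson) and 1 − 0.25 × 0.424 = 89% (k = 1). At r = 50% it is 86.5% and 79%.

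**Step 5: direction.** Let p be the share of readings at or before baseline in each arm, δ a constant treatment effect and τ the mean change common to both arms. If those readings carry neither, the expected difference between arms is (1 − p_PAL)(δ + τ) − (1 − p_EUC)τ = (1 − p_PAL)δ − (p_PAL − p_EUC)τ. With equal shares the effect shrinks towards zero. With unequal shares the second term can have either sign.

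**The case against.** The strongest reply is about size. Blood pressure is one of several Aim 1b outcomes, and the Aim 1 method places the main comparison at 12 months. There the Poisson share is 2.7% of remote values, and even spacing gives none. The larger shares rest on a spread of visit rates that no document supports. The rule also accepts any VA visit, whereas 3.6 a year counts primary care only. Blood tests are planned at 6 and 12 months with no remote route described, so a Veteran may well come in near the time point. These points stand, and they make the problem modest at 12 months if attendance is regular or random and the effect is immediate. They do not supply a date limit.

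A second reply is that the linear build-up figures mostly reflect post-baseline readings that have aged, a wider matter than readings from before treatment. That is fair. Those figures describe the total dilution under the rule, and the fix below removes only part of it.

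A third concerns arm balance. The PAL description says "the PACT teamlet will receive CPRS reminders to discuss the goals with the patients when they return for their regularly scheduled PC visits". The Enhanced Usual Care description says "Participants will follow-up with their PACT teamlets as needed when they return for their regularly scheduled PC visits". Neither adds visits, but hypothesis 1c expects PAL to raise MOVE! attendance. If those sessions produce charted readings, the shares differ by arm. The documents do not say, so the direction stays open.

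Lastly, the charted value could be the in-person baseline study reading itself. Data Storage/Security says of research activities "The following will all take place in private room at the Brooklyn VA with the PI and/or research staff", but its list does not name blood pressure, and no section says that study readings are charted. This remains only a possibility. A reading from an earlier clinic visit would carry no treatment effect either.

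**Conclusion.** The concern holds. Followed literally, the plan can enter a reading from baseline or earlier as an observed 6- or 12-month blood pressure, and no planned analysis would detect or correct it. Primary weight loss is not touched, since remote weight is obtained by telephone or video at each time point.

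At 3.6 visits a year the affected share of remote values is 0% to 36% at 6 months and 0% to 22% at 12 months, depending on the assumed visit pattern. The loss at 12 months is small only with an immediate effect and regular or random attendance. Bias is towards zero if attendance is equal by arm, and of uncertain direction otherwise. Confidence in the size is medium, because the remote share, visit pattern and time course of any effect are all assumed. It is a secondary-outcome matter that should be corrected because the correction is cheap.

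**What to change.** Add one sentence to the Measures section: a chart reading counts as a remote follow-up blood pressure only if it is dated after the baseline visit, and otherwise the value is missing and handled by the planned mixed model and multiple imputation. Record the reading date and visit mode at every time point, including a remote baseline, and report reading age by arm. An analysis limited to in-person readings is optional. It would need the caveat that visit mode at follow-up arises after randomisation and is partly the Veteran's choice.

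The cost is a sentence and two data fields. The chart-abstraction tool is not in the documents and may already hold the date, and charted readings can be dated retrospectively. More blood pressure values will be missing, in the shares tabulated above. That missingness is related to VA attendance, so missing at random is not assured. The planned analysis of observed versus missing and the missing-not-at-random sensitivity analyses would then cover it.

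The fix does not refresh older post-baseline readings. Under Poisson visits their mean age is 1/L − T·exp(−LT)/(1 − exp(−LT)), which is 65 days at 6 months and 91 days at 12 months. With a linear build-up, the share of effect kept rises only to 0.536/0.835 = 64% at 6 months and 0.730/0.973 = 75% at 12 months. One reading could also still serve both follow-ups. Reporting reading age shows what remains, and any narrower window is the sponsor's choice.
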